#### 6.2.4. Exploratory Endpoints

The following exploratory endpoints and correlative laboratory studies will be examined to determine the in vivo mechanism of action of the therapeutic combination, the biological effects of the combination of decitabine and eltrombopag, as well as to detect whether certain molecular or other genetic patterns can predict response to this combination:

- Genetic analysis of the mutational status of up to 53 genes known to be affected in myelodysplastic syndromes and acute leukemias prior to study start, performed through the molecular diagnostics laboratory of MD Anderson. Any remaining sample may be banked for additional future scientific research.
- Gene expression profiling and gene-specific DNA methylation may be performed in the pretreatment samples. DNA methylation is assessed using bisulfite PCR assays (i.e. COBRA or pyrosequencing analysis) and gene expression profiling by real-time PCR analysis.

## **6.3 Subsets**

### **6.3.1. Full Analysis Set**

The full analysis set will consist of all enrolled subjects. Analyses for demographics and baseline characteristics will utilize this analysis set.

### **6.3.2. Efficacy Analysis Set**

The efficacy analysis set will consist of all enrolled subjects who have received at least one 28-day cycle of investigational product. Analysis for efficacy endpoints will utilize this analysis set.

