#### **4.1.1. Study Replacement:**

All patients who receive at least one dose of the study drug will be included in the efficacy and safety analysis. For efficacy analysis, patients who drop out of the study early (i.e. before the end of cycle 1) due to treatment-related toxicities will be counted as treatment failures (i.e. non-responders). Patients will be replaced if they drop out of the study before receiving any dose of the study drug.

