### 6.2. Study Endpoints

**6.2.1. Primary Efficacy Endpoint:** The overall response rate (CR + PR + HI) based on the IWG-2006 criteria detailed below. Responses must last at least 4 weeks per definition.

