**Failure:**

- Death during treatment or disease progression characterized by worsening of cytopenias or significant increase in percentage of bone marrow blasts

**Hematologic Improvement (HI) Response Criteria\*:** responses must last at least 8 weeks

- **Erythroid response** (if pretreatment hemoglobin  $< 11g/dL$ )
  - Hemoglobin increase by  $\geq 1.5g/dL$
  - Relevant reduction of units of RBC transfusions by an absolute number of at least 4 RBC transfusions/8 wk compared with the pretreatment transfusion number in the previous 8 wks. Only RBC transfusions given for a Hgb of  $\leq 9.0 g/dL$  pretreatment will count in the RBC transfusion response evaluation
- **Platelet response** (if pretreatment platelets  $< 100 \times 10^9/L$ )
  - Absolute increase of  $\geq 30 \times 10^9/L$  for patients starting with  $> 20 \times 10^9/L$  platelets
  - Increase from  $< 20 \times 10^9/L$  to  $> 20 \times 10^9/L$  and by at least 100%
- **Neutrophil response** (if pretreatment  $< 1.0 \times 10^9/L$ )
  - At least 100% increase and an absolute increase of  $> 0.5 \times 10^9/L$

\*Pretreatment counts averages of at least 2 measurements (not influenced by transfusions) for at least one week

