## 8. Statistical Considerations

This is an open label, phase II clinical trial to evaluate the efficacy of eltrombopag in combination with decitabine as a frontline therapy in patients with Intermediate-2 or High-Risk Myelodysplastic Syndrome (MDS). A total of 40 patients will be accrued from M.D. Anderson Cancer Center (MDACC), at a rate of 2-3 patients per month.

The primary endpoint is the overall response rate (ORR) based on the IWG-2006 criteria, which includes complete remission (CR), partial remission (PR), and hematologic improvement (HI). Patients' overall response will be assessed during the first four 28-day cycles of treatment. Patients who drop off the study early due to treatment-related toxicities will be counted as treatment failures (i.e., non-responders).

The method of Thall, Simon and Estey [1995] will be used for futility and toxicity monitoring for this study. The target overall response rate is 60% and the following futility stopping rule will be applied in cohort size of 10, starting from the 10th patient:  $\text{prob}\{p(\text{ORR}) < 0.6\} > 0.95$ , where  $p(\text{ORR})$  denotes the overall response rate. That is, the trial will be stopped early due to futility, if during the study we determine that there is more than 95% chance that the ORR is less than 60%. Assuming that the prior distribution of  $p(\text{ORR})$  is beta (1.2, 0.8), the stopping boundaries corresponding to this futility monitoring rule are shown below in Table 1. The operating characteristics (OCs) for this futility stopping rule are summarized in Table 2. The design software Multic Lean Desktop (version 1.2.0) developed by the Department of Biostatistics at M. D. Anderson Cancer Center (MDACC) was used to generate the futility stopping boundaries and the

OC table. In order to utilize the software for the design, a highly informative beta (600, 400) prior was assumed to approximate the target 60% overall response rate.

Table 1. Futility stopping boundaries in cohort size of 10.

Number of patients	Stop the trial if there are this many patients achieving overall response
10	0-3
20	0-8
30	0-13

Table 2. Operating characteristics for futility monitoring in cohort size of 10 (max sample size = 40).

True ORR	Prob(stop the trial early due to futility)	Average sample size
0.3	0.971	14.8
0.4	0.775	22.0
0.5	0.391	31.3
0.6	0.105	37.5
0.7	0.015	39.6

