## 8.3. Analysis of Key Study Endpoints

The primary endpoint is overall response rate (ORR). The ORR will be evaluated along with the exact 95% confidence interval. Secondary endpoints include platelet response, durable platelet response, transformation to AML, incidence of bone marrow fibrosis, and time-to-event outcomes such as progression-free survival (PFS) and overall survival (OS). The probabilities of PFS and OS will be estimated using the method of Kaplan and Meier. The incidence rates of other binary secondary endpoints will be estimated, along with the exact 95% confidence intervals. Subjects that discontinue the study prior to having achieved a clinical response will be considered to have not had an event.

**Patients receiving growth factors other than eltrombopag (erythropoietin, GM-CSF or G-CSF) will not be considered in the HI analysis for the time periods specified in Section 4.5.3 Supportive Care Guidelines. Hemoglobin levels and platelet counts collected from patients that have received a transfusion within the last 7 days will not be considered in the analysis.**

Survival or times to failure and time to progression functions will be estimated using the Kaplan-Meier method. The two-sided log-rank test will be used to assess the differences of time to events between groups.

The total number of dose administrations, the average dose (mg), and the cumulative dose administered will be summarized by eltrombopag treatment group.

Blood chemistry and complete blood counts will be summarized by treatment group at each time point.

Additional exploratory analyses of the key study endpoints will be performed as deemed appropriate.

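### Section 6.3.2 drops patients with less than one cycle from the efficacy set, against Sections 4.1.1, 8 and 8.3; following it would inflate the primary ORR

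*Combined protocol and SAP*

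**What the plan says.** Section 6.3.2 defines the only efficacy set in the plan: "The efficacy analysis set will consist of all enrolled subjects who have received at least one 28-day cycle of investigational product". It goes on: "Analysis for efficacy endpoints will utilize this analysis set".

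Three other places treat the same patients differently:

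- **Section 4.1.1:** "All patients who receive at least one dose of the study drug will be included in the efficacy and safety analysis". It then names patients who leave before cycle 1 ends because of treatment-related toxicity and classes them as treatment failures. Only patients who were never dosed are replaced.
- **Section 8:** patients who come off early for treatment-related toxicity are non-responders. The rule stands beside the definition of the primary endpoint.
- **Section 8.3:** "Subjects that discontinue the study prior to having achieved a clinical response will be considered to have not had an event". No reason for discontinuing is specified.

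Sections 8.1 and 8.3 call for the ORR with an exact 95% confidence interval, but neither names an analysis set. Section 6.3.3 uses a one-dose rule for safety, so the one-cycle wording for efficacy is a separate and narrower restriction.

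**The concern.** The trial has one arm of 40 patients, and its primary result is a single proportion with an exact interval. The denominator is therefore part of the result, and the plan supports two. Section 4.1.1 counts cycle-1 toxicity dropouts as failures; Section 6.3.2 removes those same patients. Both cannot be followed. In an open-label study the choice could be made after responses are known, and either choice could be defended from the protocol.

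The restriction is not neutral. Patients who leave in cycle 1 through toxicity, death, progression or withdrawal are all non-responders, so removing them can only raise the ORR.

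Section 6.3.2 also leaves open whether someone whose eltrombopag was held during cycle 1, but who stayed on study, has received a 28-day cycle. Sections 4.8.3.2 and 4.8.4 both provide for such holds.

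**Working it through.** **1. Can a patient who leaves the study in cycle 1 be a responder?** Section 6.1 places the overall response assessment after at least 2 cycles. Section 6.2.1 adds "Responses must last at least 4 weeks per definition", and for hematologic improvement the criteria say "responses must last at least 8 weeks". A patient gone before the end of a 28-day cycle meets none of these, so the exit takes one from the denominator and nothing from the numerator. Section 4.1.1 does not replace dosed patients, so the denominator falls below 40.

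**2. Effect on the ORR.** Inputs: N = 40 treated (Section 8); R responders; E cycle-1 exits, all non-responders. The documents give no value for E. I assume 2, 4, 6 or 8 (5-20%) and, for illustration, R = 20.

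- All dosed patients (4.1.1): ORR = R/N
- At least one cycle (6.3.2): ORR = R/(N − E), i.e. the all-dosed ORR divided by (1 − E/N)
- Intervals are exact (Clopper-Pearson)

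| E | ORR under 6.3.2 | Exact 95% CI | Gain over 20/40 |
|---|---|---|---|
| 0 | 20/40 = 50.0% | 33.8-66.2 | 0 |
| 2 | 20/38 = 52.6% | 35.8-69.0 | 2.6 points |
| 4 | 20/36 = 55.6% | 38.1-72.1 | 5.6 points |
| 6 | 20/34 = 58.8% | 40.7-75.4 | 8.8 points |
| 8 | 20/32 = 62.5% | 43.7-78.9 | 12.5 points |

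With E = 8, a result 10 points below the 60% target is reported as above it. With R = 24 the all-dosed ORR is 60.0% (43.3-75.1), and it becomes 63.2%, 66.7%, 70.6% or 75.0%.

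**3. The opposite case.** If a subject with a cycle-1 hold stays on study, responds, and is excluded under 6.3.2, one responder is lost from both counts: 19/39 = 48.7% (32.4-65.2), below 50.0%. The upward direction is certain only for study exits.

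**4. Effect on futility monitoring.** First, the plan's own figures. With a beta(1.2, 0.8) prior and x responders among n patients, the posterior is beta(1.2 + x, 0.8 + n − x). The rule stops when P(ORR < 0.6) exceeds 0.95:

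- n = 10: 0.962 at x = 3, 0.878 at x = 4
- n = 20: 0.957 at x = 8, 0.901 at x = 9
- n = 30: 0.963 at x = 13, 0.922 at x = 14

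These give the Table 1 boundaries of 3, 8 and 13. Exact binomial recursion over the three looks gives stop probabilities of 0.971, 0.775, 0.391, 0.105 and 0.015, with average sample sizes of 14.8, 22.0, 31.3, 37.5 and 39.6, at true ORRs of 0.3 to 0.7. Table 2 is reproduced.

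Table 1 compares responder counts. With looks at 10, 20 and 30 *treated* patients, early exits are already counted as non-responders, and the stop probability at a true ORR of 0.50 stays at 0.391. If the looks were instead timed by 10, 20 and 30 *evaluable* patients under 6.3.2, the response probability per evaluable patient would be 0.50/(1 − d), where d is the exit fraction:

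| d | 0.50/(1 − d) | Stop probability |
|---|---|---|
| 5% | 0.526 | 0.295 |
| 10% | 0.556 | 0.205 |
| 15% | 0.588 | 0.127 |
| 20% | 0.625 | 0.068 |

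The documents do not say that the looks are timed this way, so this series is conditional.

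**The case against.** The best counter-argument is that a sensible reading already exists. Section 4.1.1 deals specifically with patients who leave before the end of cycle 1, Section 8 restates the failure rule next to the primary endpoint, and Section 8 never refers to the set in 6.3.2. A statistician might well use all dosed patients. But 6.3.2 says in terms that it governs efficacy endpoints, and no sentence ranks the two rules.

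Other points, and what stands of them:

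- **Only the conflict with 4.1.1 is head-on.** Correct. Sections 8 and 8.3 define no analysis set; they conflict because they keep patients whom 6.3.2 removes. The 8.3 sentence follows text on secondary and time-to-event endpoints, so its scope is not perfectly clear, though its reference to clinical response fits the ORR.
- **Stopping the drug is not the end of observation.** Section 5 schedules a marrow at the end-of-treatment visit, weekly blood counts for 4 weeks after eltrombopag stops, and a later safety visit, so the 4-week duration alone might not rule out a response. This is fair for patients who stop the drug but stay under observation, and it is why the claim of direction is confined to study exits. For those, Section 6.1 settles the matter.
- **The size rests on an assumed exit rate, and no decision rule changes.** Both are true on the plan's own terms: the final analysis is an estimate with no success threshold, and futility is untouched if looks count treated patients. The estimate is nevertheless the trial's primary result.

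**Conclusion.** The concern holds. Sections 6.3.2 and 4.1.1 give incompatible denominators for the primary endpoint, and Sections 8 and 8.3 side with 4.1.1. If 6.3.2 is followed, each patient who leaves the study in cycle 1 raises the ORR. The gain is 2.6 to 12.5 points in the illustration with 20 responders among 40 and an assumed 5-20% exit rate, and zero if nobody leaves. The bias could run the other way only for patients excluded because of a cycle-1 hold who stay on study and respond. The contradiction does not depend on the exit rate and should be resolved before the ORR is analysed.

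**What to change.** Replace the definition in Section 6.3.2 with wording such as: *Efficacy analysis set: every enrolled patient given one or more doses of study drug. Anyone who leaves the study with no documented response, whatever the reason, counts as a non-responder.* The first sentence follows 4.1.1 and the second follows 8.3. The toxicity-only failure rules in 4.1.1 and 8 then become special cases of the general rule.

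Add one sentence to Section 8 saying that the final ORR, its confidence interval and the futility looks at 10, 20 and 30 patients all use this set.

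If an analysis of patients with at least one cycle is wanted, keep it as a labelled sensitivity analysis and define what counts as a 28-day cycle when doses are held or missed.

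The cost is one reworded section and one added sentence, with no extra patients or data. The reported ORR may be less favourable than under the present 6.3.2 by the gains tabulated above.

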### **6.3.3. Safety Analysis Set**

The safety analysis set will consist of all subjects who received at least 1 dose of investigational product. Subjects will be analyzed according to the treatment actually received. Analysis for safety endpoints will utilize this analysis set.

## **7. Regulatory and Reporting Requirements**

### **7.1. Informed Consent**

Before a subject's participation in the clinical study, the investigator is responsible for obtaining written informed consent from the subject or legally acceptable representative after adequate explanation of the aims, methods, anticipated benefits, and potential hazards of the study and before any protocol-specific screening procedures or any investigational products are administered. A legally acceptable representative is an individual or other body authorized under applicable law to consent, on behalf of a prospective subject, to the subject's participation in the clinical study.

The acquisition of informed consent should be documented in the subject's medical records, and the informed consent form should be signed and personally dated by the subject or a legally acceptable representative and by the person who conducted the informed consent discussion. The original signed informed consent form should be retained in accordance with institutional policy, and a copy of the signed consent form should be provided to the subject or legally acceptable representative.

### **7.2. Independent Ethics Committee/Institutional Review Board**

A copy of the protocol, proposed informed consent form, other written subject information, and any proposed advertising material must be submitted to the IEC/IRB for written approval. A copy of the written approval of the protocol and informed consent form must be received by Novartis Oncology before recruitment of subjects into the study and shipment of investigational product.

The investigator must submit and, where necessary, obtain approval from the IEC/IRB for all subsequent protocol amendments and changes to the informed consent form. The investigator should notify the IEC/IRB of deviations from the protocol or serious adverse events occurring at the site and other adverse event reports received from Novartis Oncology, in accordance with local procedures.

The investigator will be responsible for obtaining annual IEC/IRB approval/renewal throughout the duration of the study. Copies of the investigator's reports and the IEC/IRB's continuance of approval must be sent to. Novartis Oncology

### **7.3 Subject Confidentiality**

The investigator must ensure that the subject's confidentiality is maintained. On documents submitted to Novartis Oncology, subjects should be identified by their study number only. Documents that are not for submission to Novartis Oncology (eg, signed informed consent forms) should be kept in strict confidence by the investigator.

In compliance with ICH GCP Guidelines, it is required that the investigator and institution permit authorized representatives of the company, of the regulatory agency(s), and the IEC/IRB direct access to review the subject's original medical records for verification of study-related procedures and data. Direct access includes examining, analyzing, verifying, and reproducing any records and reports that are important to the evaluation of the study. The investigator is obligated to inform and obtain the consent of the subject to permit named representatives to have access to his/her study-related records without violating the confidentiality of the subject.

### **7.4. Protocol Amendments and Study Termination**

Protocol amendments, except where necessary to eliminate an immediate hazard to subjects, must be made only with the prior approval of Novartis Oncology. Agreement from the investigator must be obtained for all protocol amendments and amendments to the informed consent form. The IEC/IRB must be informed of all amendments and give approval. The investigator must send a copy of the approval letter from the IEC/IRB to Novartis Oncology.

Both Novartis Oncology and the investigator reserve the right to terminate the study according to the study contract. The investigator should notify the IEC/IRB in writing of the study's completion or early termination and send a copy of the notification to Novartis Oncology.

Subjects may be eligible for continued treatment with investigational product by extension protocol or as provided for by the local country's regulatory mechanism. However, Novartis Oncology reserves the unilateral right, at its sole discretion, to

determine whether to supply the investigational product, and by what mechanism, after termination of the trial and before it is available commercially.

## **7.5. Study Documentation and Archival**

The investigator should maintain a list of appropriately qualified persons to whom he/she has delegated study duties. All persons authorized to make entries and/or corrections on case report forms will be included on the Delegation of Authority Form.

Source documents are original documents, data, and records from which the subject's case report form data are obtained. These include but are not limited to hospital records, clinical and office charts, laboratory and pharmacy records, diaries, microfiches, radiographs, and correspondence. Case report form entries may be considered source data if the CRF is the site of the original recording (ie, there is no other written or electronic record of data). In this study, case report forms calculating IPSS may be used as source documents for IPSS risk category assignment.

The investigator and study staff are responsible for maintaining a comprehensive and centralized filing system of all study-related (essential) documentation, suitable for inspection at any time by representatives from Novartis Oncology and/or applicable regulatory authorities. Elements should include:

- Subject files containing completed case report forms, informed consent forms, and subject identification list

Study files containing the protocol with all amendments, investigator's brochure, copies of prestudy documentation and all correspondence to and from the IEC/IRB and Novartis Oncology

- - Proof of receipt, Investigational Product Accountability Record, Return of Investigational Product for Destruction, Final Investigational Product Reconciliation Statement, and all drug-related correspondence

In addition, all original source documents supporting entries in the case report forms must be maintained and be readily available. No study document should be destroyed without prior written agreement between Novartis Oncology and the investigator. Should the investigator wish to assign the study records to another party or move them to another location, he/she must notify Novartis Oncology in writing of the new responsible person and/or the new location.

## **7.6. Serious Adverse Event Reporting (SAE):**

See Section 6.2.2.1 for detailed information regarding SAE definitions.

It is the responsibility of the PI and the research teams to ensure serious adverse events are reported according to the Code of Federal Regulations, Good Clinical

Practices, the protocol guidelines, the sponsor's guidelines, and Institutional Review Board policy.

All events occurring during the conduct of a protocol and meeting the definition of a SAE must be reported to the IRB in accordance with the timeframes and procedures outlined in "The University of Texas M. D. Anderson Cancer Center Institutional Review Board Policy for Investigators on Reporting Unanticipated Adverse Events for Drugs and Devices". Unless stated otherwise in the protocol, all SAEs, expected or unexpected, must be reported to , regardless of attribution (see Section 6.2.2.3). SAE reporting will be done according to 21 CFR 312.32(c)(1)(iv) ("Sponsor must report any clinically important increase in the rate of a serious adverse reaction over that listed in the protocol or investigator brochure.").

The descriptions and grading scales found in the revised NCI Common Terminology *Criteria for Adverse Events (CTCAE) version 4.0* will be utilized for adverse event reporting. (<http://ctep.cancer.gov/reporting/ctc.html>).

